5.6.8. Physical Examination

The physical examination data will be presented in by-patient listings.

5.6.9. ECOG Performance Status

The ECOG PS scores and the grades from 0 to 5 are described in [Table 9](#).

The ECOG performance status score will be summarized by presenting the number and percentage of each score by scheduled time point. A shift table will be presented to display the shift from baseline grade to the worst post-baseline grade. Change from baseline to post-baseline of ECOG performance status at each scheduled visit will be presented in a shift table. A patient level listing will also be presented.

Table 9: Grade Categories of Eastern Cooperative Oncology Group Score

Grade	ECOG
0	Fully active, able to carry on all pre-disease performance without restriction.
1	Restricted in physically strenuous activity but ambulatory and able to carry out work of a light or sedentary nature (e.g., light housework, office work).
2	Ambulatory and capable of all self-care but unable to carry out any work activities. Up and about more than 50% of waking hours.
3	Capable of only limited self-care, confined to bed or chair more than 50% of waking hours.
4	Completely disabled. Cannot carry on any self-care. Totally confined to bed or chair.
5	Dead.

5.6.10. Pregnancy Test

If the patient is female and of childbearing potential, a serum or urine human chorionic gonadotrophin (human chorionic stimulating hormone) test will be performed at scheduled time point. For screening, serum test is required. Pregnancy test result will be presented in by-patient listing.

5.6.11. Echocardiography/MUGA

Left ventricular ejection fraction (LVEF) by echocardiography or MUGA will be summarized with descriptive statistics by scheduled time point. Changes from baseline will be summarized in a similar manner. Shift table of echocardiography/MUGA (multiple gated acquisition) is presented by scheduled time point. Also, it will be presented in by-patient listing.

5.6.12. Ophthalmological Examination

The result of ophthalmological examination will be summarized with the number and percentage of each category by scheduled time point, examination, and tested eye (left, right). Also, it will be presented in by-patient listing.

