1.3. SCHEDULE OF EVENTS

Table 1: Schedule of Events for Phase 1 (Parts A and B)

Procedure	Screening Period Within 28 Days prior to first dose	Treatment Period							Follow-up Period		Notes
		PK Lead-in ^a	Cycle 1 (21 days)			Cycle 2 (21 days)		Cycles ≥ 3 (21 days)	Safety Follow-up ^b	Survival Follow-up	
		Day -3	Day 1	Day 8 (± 1 day)	Day 15 (± 3 days)	Day 1 (± 3 days)	Day 8 (± 3 days)	Day 1 (± 3 days)	30 (+3) days after last dose		
EGFR C797S status (pre-screening informed consent)	See Notes										Only if central pre-screening done. Can be done any time prior to screening.
Written informed consent (main study)	X										To be obtained prior to any study related procedures.
Review inclusion / exclusion criteria	X										All patients in Part A2 and B must have documented C797S EGFRmt. See Section 4.1 and Section 4.2
Demographics/ Medical history	X										Including prior antitumor treatment
Physical examination	X	X	X	X		X		X	X		Within 24 hours prior to dosing. May be symptom directed during treatment period. Examination of skin should be performed at each timepoint. See Section 7.1
Ophthalmological examination	X	As clinically indicated							X		See Section 7.1.5
Height and weight	X	X	X			X		X	X		Height at screening only
Vital signs	X	X	X	X	X	X	X	X	X		Heart rate, blood pressure, and body temperature. See Section 7.1
Hematology	X	X	X	X	X	X	X	X	X		Assessment prior to first day of dosing may be done up to 72 hours prior to dosing

											(Section 7.1.4) All other assessments may be done within 24 hours prior to dosing See Section 7.1
Chemistry	X	X	X	X	X	X	X	X	X		Assessment prior to first day of dosing may be done up to 72 hours prior to dosing (Section 7.1.4) All other assessments may be done within 24 hours prior to dosing See Section 7.1
Coagulation	X	X	X			X		X	X		Assessment prior to first day of dosing may be done up to 72 hours prior to dosing (Section 7.1.4) All other assessments may be done within 24 hours prior to dosing See Section 7.1
Urinalysis	X	X	X			X		X	X		Assessment prior to first day of dosing may be done up to 72 hours prior to dosing (Section 7.1.4) All other assessments may be done within 24 hours prior to dosing. See Section 7.1
Pregnancy test	X	X	(X)			X		X			For WOCBP only: Serum pregnancy test required at screening only. See Section 7.1 (X) not required for patients in Part A1

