2.2.1.7. Eye Disorders

In nonclinical studies, atrophy of corneal epithelium was observed.

Potential side effects and risks anticipated are keratitis, corneal erosion, corneal ulcer, vision blurred, corneal opacity, and eye pain. Monitoring of patients for eye disorders will be conducted by ophthalmological examinations at baseline and any time during study treatment if clinically indicated. Patients should be advised to contact their study physician if experiencing any change in vision.

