7.1.3. Cardiac Function Evaluation

The commonly available imaging modalities (ECHO 2D, MUGA) will be used for the evaluation of LVEF evolvement during therapy with TAS3351 to detect presence of cardiotoxicity defined by the European Society of Cardiology as a decrease in LVEF of >10% points to a value below 50%.²⁹ Imaging will be performed by the cardiologist or qualified delegate per the Schedule of Activities ([Table 1](#)). Additional on-study evaluation may be performed as needed based on physician judgment and/or symptoms or signs of LV dysfunction. Each evaluation will encompass:

- LVEF assessment using MUGA, conventional 2DE biplane Simpson method or 3DE, if available
- Clinical symptoms of Congestive Heart Failure (CHF) will be noted and graded according to NYHA

Signs of CHF will be detected by routine clinical examination, including auscultation to detect S3 gallop, tachycardia, or both.

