5.6.4. Clinical Laboratory Evaluations

Clinical laboratory results will be summarized using SI Units. Laboratory measurements will be summarized for each parameter. Descriptive statistics (n, mean, standard deviation, median, minimum, and maximum) will be presented for clinical chemistry, hematology, and coagulation parameters at each scheduled visit. Change from baseline will be summarized in a similar manner.

Laboratory test results will be graded by NCI CTCAE (Version 5.0). Shift tables will be presented for each laboratory parameter to display the shift from baseline grade to the worst post-baseline grade. Summary tables will be provided presenting the number and percentage of patients for each laboratory test by baseline grade and worst post-baseline grade. All post-baseline assessments (including unscheduled visits) will be used to determine the worst post-baseline grade.

For qualitative urinalysis parameters and summary tables will be provided presenting the number and percentage of patients for each parameter and scheduled visit. If any quantitative urinalysis parameters will be collected, descriptive statistics will also be presented at each parameter and scheduled visit.

All clinical laboratory data will be presented in by-patient listings.

The laboratory tests of hematology, serum chemistry, coagulation, and urinalysis are listed in [Table 8](#).

Table 8: Laboratory Tests

Assessment	Test Items
Hematology	Red blood cell (RBC) count, hemoglobin, hematocrit, platelets, white blood cell (WBC) count with differential, neutrophils (ANC), lymphocytes, monocytes, eosinophils, basophils
Serum chemistry	AST, ALT, ALP, total bilirubin, direct bilirubin, albumin, lipase, amylase, LDH, triglyceride, total cholesterol, creatinine, BUN, Na, K, Cl, Serum Calcium, Ca (corrected value), Mg, blood glucose, C reactive protein (CRP), creatinine clearance (if there is a measured value, use the measured value) or eGFR. For a calculated CrCl value, use the Cockcroft-Gault formula: Male: $CrCl = \frac{(140 - [insert\ age\ in\ years]) \times [insert\ weight\ in\ kg]}{72 \times [insert\ serum\ creatinine\ in\ mg/dL]}$ Female: $CrCl = [\frac{(140 - [insert\ age\ in\ years]) \times [insert\ weight\ in\ kg]}{72 \times [insert\ serum\ creatinine\ in\ mg/dL]}] \times 0.85$
Coagulation	PT-INR, APTT, and fibrinogen

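### The SAP has no any-time or worst post-baseline summary for eye findings or LVEF, so results from clinically indicated examinations reach only listings and, if clinically significant, adverse event tables

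*SAP*

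**What the plan says.** SAP Table 1 names ophthalmologic assessment and echocardiography/MUGA under the primary objective of Part A and under the secondary safety objective of Part B. Their dedicated analyses are short.

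- **Eye (SAP 5.6.12):** results are "summarized with the number and percentage of each category by scheduled time point, examination, and tested eye (left, right"). A listing is added: "Also, it will be presented in by-patient listing".
- **LVEF (SAP 5.6.11):** values and changes from baseline are summarised by scheduled time point, and "Shift table of echocardiography/MUGA (multiple gated acquisition) is presented by scheduled time point". A by-patient listing is added here too.

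The protocol sets the timing of these assessments for Parts A and B, the parts that the SAP covers.

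- **Eye (protocol Table 1):** an examination at screening and one at safety follow-up. The entry for the whole treatment period is "As clinically indicated". Protocol 2.2.1.7 describes the monitoring as examinations "at baseline and any time during study treatment if clinically indicated".
- **LVEF (protocol Table 1 and 7.1.3):** a screening scan, then scans from Cycle 4 every 4 cycles or when clinically indicated, with none marked at safety follow-up. Section 7.1.3 also allows extra scans prompted by symptoms or signs. It gives the event that imaging should detect as "a decrease in LVEF of >10% points to a value below 50" percent.

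For laboratory data the SAP takes another approach in 5.6.4: "All post-baseline assessments (including unscheduled visits) will be used to determine the worst post-baseline grade".

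**The concern.** A summary by scheduled time point suits an assessment whose informative results come at scheduled visits. Eye examinations during dosing are the opposite case: every one is prompted by a clinical indication, so none belongs to a scheduled visit. For LVEF, scheduled scans do exist, but they start late and are widely spaced, and the protocol foresees symptom-prompted scans in between.

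At stake is how complete the safety summary by dose level is for two named endpoints. A reader of the eye and LVEF tables could see few abnormalities at a dose level although abnormal results were recorded between scheduled assessments. A listing holds those results but gives no count, percentage or comparison across doses. Such a comparison matters because Part B may randomise patients between two dose levels.

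**Working it through.** The documents state no figure on this point that could be reproduced. The check compares the table rules with the schedule and then does a small timing calculation.

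**1. Scheduled assessments, Parts A and B** (protocol Table 1, 21-day cycles). Cycle k Day 1 falls (k − 1) × 21 days after Cycle 1 Day 1.

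- Eye: 0 scheduled examinations during dosing and 1 scheduled after baseline (safety follow-up). A table by scheduled time point can therefore show only screening and safety follow-up.
- LVEF: the first scheduled post-baseline scan is Cycle 4 Day 1, 3 × 21 = 63 days after Cycle 1 Day 1 (Day 64). The next is Cycle 8 Day 1, 7 × 21 = 147 days after it (Day 148). The interval is 147 − 63 = 84 days.

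**2. Where a result goes under the SAP as written**

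| Result | Eye or LVEF summary table | Listing | AE tables |
|---|---|---|---|
| Eye finding during dosing, resolved before safety follow-up | No | Yes | If clinically significant |
| Eye finding still present at safety follow-up | Yes, at that visit | Yes | If clinically significant |
| LVEF fall on an unscheduled scan, recovered by the next scheduled scan | No | Yes | If judged clinically significant |
| LVEF fall on an unscheduled scan, treatment stopped before Cycle 4 | No | Yes | If judged clinically significant |
| LVEF fall still present at a scheduled scan | Yes, at that scan | Yes | If judged clinically significant |

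**3. How many patients might stop before the first scheduled LVEF scan.** The documents give no time on treatment for TAS3351. As an assumption, take it as exponential with median m. For m, borrow the 4 to 5 month median PFS that protocol 2.1.1 gives for platinum chemotherapy after osimertinib. SAP 5.6.1.1 sets 1 month = 30.4375 days.

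- 63 / 30.4375 = 2.07 months; 147 / 30.4375 = 4.83 months.
- Proportion still on treatment at t: S(t) = exp(−ln 2 × t / m).

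| m (months) | S(2.07) | Stop before C4D1 | S(4.83), reach C8D1 |
|---|---|---|---|
| 4 | 0.699 | 30% | 43% |
| 4.5 | 0.727 | 27% | 48% |
| 5 | 0.751 | 25% | 51% |

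For patients who stop before Cycle 4 Day 1, an unscheduled scan is the only LVEF that could be obtained during dosing.

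**4. Comparison within the SAP.** Laboratory data have a shift to the worst post-baseline grade that expressly includes unscheduled visits (5.6.4). ECG interpretation (5.6.6) and ECOG status (5.6.9) each have a shift to the worst post-baseline value. Eye findings and LVEF have neither.

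**5. The 7.1.3 event.** It combines a change (more than 10 points) with a level (below 50%). The descriptive statistics in 5.6.11 do not count patients who meet both conditions. The shift table is by scheduled time point, its categories are not stated, and no other SAP table is assigned the count.

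**The case against.** The strongest reply is that nothing is lost from the report. Both SAP sections end with a by-patient listing. Protocol 7.1.5 requires every clinically significant eye finding to be reported as an AE, and SAP 5.6.2 tabulates treatment-emergent AEs by cohort, class, term and grade with no visit restriction. This stands. A reader might infer that symptomatic cases are left out of the report, and the documents do not support that. The AE route is less firm for LVEF. Protocol 10.1.2 covers clinically significant abnormal safety assessments in general, does not name LVEF, and leaves the call to the investigator. A fall meeting the 7.1.3 definition without symptoms therefore need not become an AE. Laboratory abnormalities also have an AE route, and the SAP still gives them a worst-value table.

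Three further replies stand in part.

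- The SAP says by scheduled time point and never says only. Exclusion is inferred from the lack of any other rule, and SAP 7.4 refers remaining data-handling rules to a separate document that is not available here. Even so, 5.6.4 states its rule for unscheduled visits outright, and a programmer working from 5.6.11 and 5.6.12 would produce by-visit tables.
- The tables are not blind. The safety follow-up eye examination and the LVEF scans from Cycle 4 are tabulated, so a persistent abnormality is seen. SAP 7.2 counts evaluations up to 30 days after the last dose as on-treatment, so a follow-up examination done by then is both scheduled and on-treatment. It would be wrong to say that all on-treatment eye examinations fall outside the table.
- Protocol 7.1.3 cites the LVEF threshold as what imaging should detect and does not make it an analysis endpoint. That is correct, but the stated purpose of the imaging is still not summarised anywhere.

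**Conclusion.** The gap holds as a shortcoming in two safety summaries. Under the SAP as written, results of clinically indicated eye and LVEF examinations reach by-patient listings and, when judged clinically significant, AE tables, but no eye or LVEF summary by dose level. The gap is clearest for the eye, with no scheduled examination during dosing. For LVEF the tables are incomplete before Day 64 and within each 84-day interval. The 7.1.3 event is counted nowhere.

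Two stronger readings should be set aside.

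- A reader might take the 25% to 30% as the share of cardiac cases missed. It is only a modelled share of patients stopping before Cycle 4 Day 1, resting on an exponential form and a chemotherapy PFS benchmark. The documents give no rate of unscheduled scans or of LVEF falls.
- A reader might infer that the choice of RP2D rests on these tables. Protocol 12.7.4.1 bases it on accumulated DLT data and the totality of data, and no section ties it to the by-visit eye or LVEF tables.

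No DLT or efficacy estimate is affected.

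**What to change.** In SAP 5.6.11 and 5.6.12:

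1. Add shift tables from baseline to the worst post-baseline result, by dose level, using all post-baseline assessments including unscheduled ones, in line with 5.6.4.
2. In 5.6.11, add the number and percentage of patients, by dose level, who meet the protocol 7.1.3 LVEF definition at any post-baseline assessment.
3. State the window. The safety follow-up visit in protocol Table 1 is at 30 (+3) days after the last dose, whereas SAP 7.2 closes the on-treatment window at 30 days. The new tables should say whether an examination on days 31 to 33 counts.
4. Footnote that the percentages rest partly on symptom-prompted examinations. Patients without symptoms were examined less often, so the figures are not incidence under uniform monitoring.

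The cost is SAP wording and a few extra tables. The assessments are already planned and listed, so no new data collection, visit or design change is needed. The existing by-visit tables can stay.

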5.7. Pharmacokinetic / Pharmacodynamic Analyses

All PK analyses will be conducted using the PK population. If deviation and/or interruption of study drug administration are considered to affect the PK, the data will be excluded from summary statistics and statistical evaluations.

5.7.1. Plasma Concentration Data

5.7.1.1. Concentration Summarization

The lower limit of quantification (LLOQ) and the upper limit of quantification of TAS3351 and TAS-05-14317 are 0.5 and 1000 ng/mL, respectively in plasma. Individual plasma concentration data and actual time after dose will be listed by study period, dose level, patient, study day, and nominal collection time. The actual time after dose will be calculated as “actual date and clock time of blood collection” – “actual date and clock time of dosing”. Concentrations reported as below or above the quantification limits (BQL or AQL) will be reported as “BQL” or “AQL” in the listing of individual concentration data, respectively.

Plasma concentrations at each PK blood sampling day and time included in the study protocol will be summarized by dose level and treatment period according to nominal collection time. The time of collection of the pre-dose sample will be set to zero. Concentrations reported as BQL or AQL will be treated as missing for the purpose of concentration summarization. When sampling times fall outside a specified window or when sampling times deviate from the nominal time by a specified percentage, concentrations may be excluded from summaries.

Descriptive statistics for plasma concentrations at each PK blood sampling day and time included in the study protocol, including number of observations (n), arithmetic mean, standard deviation (SD), coefficient of variation (CV%), minimum, median, and maximum, will be presented by dose level and treatment period according to nominal collection time. The mean, median, minimum, and maximum will be presented to the same significant digit as the original values. SD will be presented to the same decimal place as the mean. CV% will be presented to 1 decimal place.

If less than half of individual data is available at a time point, summary data will be omitted or flagged. The number of observations is defined as the number of actual, reported values as received from the bioanalytical laboratory, including <LLOQs, before any transformations are made. Any missing value due to causes such as: sample not drawn, sample not received, sample not suitable, result not reported, including possible other reasons why there is no sample analysis result, does not contribute to the count of “number of observations”.

If a patient is treated with dose-modification or dose-interruption, concentrations from this patient on next PK collection date onward may be flagged and excluded from the summary statistics if deemed as appropriate.

The concentration data may also be used for a population PK analysis as appropriate. An analysis plan for the population PK will be provided separately from this SAP.

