6.1.1. Dose Escalation

The starting dose of TAS3351 will be 50 mg QD (Table 5). The study is designed to escalate TAS3351 up to a dose of 700 mg daily based on safety and tolerability observed, with lower increments considered, if clinically relevant toxicities are observed. The upper end of 700 mg TAS3351 total daily dose levels are based on more conservative assumptions for PK predictions and non-clinical efficacy data observed. In case of toxicity, other dose levels, such as intermediate or dose levels lower than Dose Level 1, may be explored following discussion and agreement between the Sponsor and the Investigators.

Table 5: TAS3351 Dose Levels

Dose Level	Total Daily Dose (mg/d)	Absolute and % Change from Previous Total Daily Dose
-1	25	-25 mg / -50%
1 (Starting dose)	50	-
2	100	50 mg / 100%
3	200	100 mg / 100%
4	350	150 mg / 75%
5	500	150 mg / 43%
6	700	200 mg / 40%

Note: If no DLTs observed at 700 mg QD, any further dose escalation will not exceed 33% increments.

In addition, if PK, pharmacodynamic, and/or safety data indicate that splitting the dose of TAS3351 in two daily doses might be preferable (eg, due to short half-life, saturation of exposure), then twice daily (BID) dosing of TAS3351 may be explored following discussion and agreement between the Investigators and the Sponsor. In such case, the dose of the highest QD dose shown previously to be safe and tolerable will be divided into two equal doses to be taken in the morning and evening approximately 12 hours apart. Dose escalation for twice daily dosing will follow total daily doses shown in Table 5 (ie, total daily dose divided by 2 for BID dosing).

The planned dose escalation will follow a BOIN design, [REDACTED]. For further information about statistical considerations, please see Section 12.

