5.3.3. Baseline Disease Characteristics

The following nature and duration of cancer will be summarized. Listings will also be provided.

- Time since initial diagnosis (years)
= (Year of informed consent) – (Year of initial diagnosis) + 1
- Age at initial diagnosis
= (Age at the time of informed consent) – (Time since initial diagnosis)
- Time since confirmation of first metastasis (years)
= (Year of informed consent) – (Year of the first metastasis confirmed) + 1
- Cancer stage (TNM: I A1 to IV B) at the time of initial diagnosis
- Histology (Adenocarcinoma/Squamous cell carcinoma/Neuroendocrine tumors/Large cell carcinoma/Other)
- Grade of tumor (Well differentiated/Moderately differentiated/Poorly differentiated/Undifferentiated/Unknown)
- Presence and absence of CNS metastases
- New CNS metastases (yes/no)
- CNS metastases progressing after last treatment (yes/no)
- Patient with leptomeningeal disease (yes/no)
- Results of local tumor tissue/cfDNA analysis
 - Type of sample (Tumor tissue, cfDNA from blood sample)
 - Assay method (NGS, PCR, Other)
 - Type of EGFRmt (C797S/ Exon 19 Deletion/ Exon 20 insertion/ E709X/ G719X/ L858R/ L861Q/ L861R/ S768I/ T790M/ Amplification/ Other)

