5.6.1. Extent of Exposure

5.6.1.1. Administration of Study Drug

The following parameters will be summarized. These will also be summarized by dose group.

- Duration of treatment
- Number of patients with treatment duration (<1 months, >=1-3 months, >=3-6 months, >=6-9 months, >9 months)
- Cumulative Dose
- Number of Cycles Treated
- Dose intensity
- Relative dose intensity (RDI)

Duration of treatment will be calculated as: (Date of last dose – Date of first dose + 1). For categorical summary, 1 month is set as 30.4375 days.

Cumulative dose

Cumulative dose (mg) is sum of the doses administered to a patient during the treatment period.

Dose intensity

Dose intensity (mg/day) is the cumulative dose (mg) divided by the duration of treatment (days).

Relative dose intensity (RDI)

Relative dose intensity (%) is calculated as cumulative dose (mg) divided by total planned dose (mg), where total planned dose is the treatment duration multiplied by planned dose level.

A by-patient listing of dose of study drug will also be provided.

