In addition, the predicted mean change from baseline QTcF (in milliseconds) will be presented for each dose level using the same linear mixed-effects models as described above, where plasma concentration is specified as the geometric mean C_{\max} for each dose level on a specific visit. The predicted mean change from baseline QTcF (in milliseconds) may also be presented for each dose level using the same linear mixed-effects models as described above, where plasma concentration is specified as the maximal observed concentration at each dose level. A double-sided 90% confidence interval for the predicted mean Δ QTcF will also be presented.

The following model assumptions will be evaluated by the indicated exploratory plots:

- Assumption 1: No drug effect on HR
 - Time course of mean Δ HR effects by dose will be plotted
- Assumption 2: QTcF interval is independent of HR
 - QTcF vs RR will be plotted
 - The adequacy of the correction formula will be assessed by determining the linear relationship of QTcF to RR. Adequacy will be evaluated based on the population QTcF:RR slope. If QTcF is determined to be an inadequate correction, then another fixed-formula rate correction may replace the primary endpoint of QTcF
- Assumption 3: No time delay between drug concentrations and Δ QTcF
 - Time course of mean concentrations and mean Δ QTcF by dose will be plotted
- Assumption 4: Linear C-QTcF relationship
 - Δ QTcF versus concentration will be plotted with a trend line included

If significant hysteresis is found, another model (e.g., Emax model, effect-compartment model) should be explored.

Goodness-of-fit plots, including but not limited to Model predicted vs observed $\Delta Q T c F$, Quartile-Quartile plot of residuals, Concentrations vs residuals, Baseline $Q T c F$ vs residuals, Time vs residuals, and Quantiles of concentrations and $\Delta Q T c F$ overlaid with slope of final model and when relevant for key stages during model development may be presented.

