5.7.2. Plasma PK Parameters

5.7.2.1. PK Parameter Calculation

For the Dose Escalation part (Part A1) of the study, PK parameters will be calculated by standard noncompartmental analysis (NCA) on Day -3 of PK Lead-in (for QD dosing) or Day 1 (for BID dosing, if applicable) and Day 15 (for both QD and BID dosing, if applicable) of Cycle 1.

The calculation of PK parameters in plasma will be based on the actual time after the dosing. The time of collection of the pre-dose sample will be set to zero for calculating PK parameters. The plasma concentration data for the calculation of PK parameters will be handled as described in Section 5.7.1.1 except that plasma concentrations below the LLOQ appearing in terminal time-points will be treated as missing.

Plasma PK parameters will be estimated as follows:

- C_{\max} (Maximum observed concentration);
- T_{\max} (Time of maximum observed concentration);

C_{\max} and T_{\max} are obtained from experimental observations. If C_{\max} occurs at 2 or more time points, T_{\max} is assigned to the time of the earliest occurrence. In determining T_{\max} , the actual time of the plasma sample relative to the dosing time will be used.

- AUC_{last} (Area under the curve from the time of dosing to the time of last quantifiable concentration);
- AUC_n (Area under the curve from the time of dosing to time n);

AUCs will be calculated using the linear log trapezoidal rule. AUC_n will be calculated by the program as a partial area depending on the dosing interval. Prior to calculating AUCs and $T_{1/2}$ (terminal elimination half-lives), the individual plasma concentrations by time profiles are evaluated on an individual basis as to their suitability for inclusion in these calculations. In calculating AUCs, plasma concentrations that are listed as BQL are treated as missing, except for the following cases: for single-dose profiles, BQL concentrations prior to the first quantifiable concentration will be set to 0; for multiple-dose profiles, BQL concentrations at the beginning of the profile may be set to 0 or C_{\min} . The pre-dose sampling time will be set to 0. For single-dose profiles, the concentration at pre-dose will be set to 0.

- $T_{1/2}$ (Terminal half-life)

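### Disease duration and lead-in relative dose intensity are mis-derived in the SAP as written; Cmax would be too if any concentration is reported above 1000 ng/mL

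*SAP*

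**What the plan says.** All three rules are in the SAP, which covers Parts A and B.

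- **Disease history (SAP 5.3.3).** Time since initial diagnosis, in years, takes the calendar year of consent, subtracts the calendar year of diagnosis and adds one; the formula ends "Year of initial diagnosis) + 1". Time since first metastasis is built the same way. Age at diagnosis is age at consent less the derived time since diagnosis.
- **Relative dose intensity, RDI (SAP 5.6.1.1).** RDI is cumulative dose over total planned dose, and "total planned dose is the treatment duration multiplied by planned dose level". Duration is last dose date minus first dose date plus one. SAP Table 2 starts Part A1 treatment at the PK lead-in. Protocol Table 1, footnote a, makes that lead-in one dose, three days before continuous dosing begins.
- **Concentrations above the assay range (SAP 5.7.1.1 and 5.7.2.1).** The range is stated thus: "The lower limit of quantification (LLOQ) and the upper limit of quantification of TAS3351 and TAS-05-14317 are 0.5 and 1000 ng/mL, respectively in plasma". For results outside it: "Concentrations reported as BQL or AQL will be treated as missing for the purpose of concentration summarization". Section 5.7.2.1 extends this to the noncompartmental analysis: "The plasma concentration data for the calculation of PK parameters will be handled as described in Section 5.7.1.1". Its exceptions concern only values below the lower limit. Cmax and Tmax "are obtained from experimental observations".

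**The concern.** None of the three rules measures quite what its label says.

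- The duration formula gives 2 years for a diagnosis in December 2022 and consent in January 2023.
- The RDI denominator treats days on which no drug was scheduled as days of planned drug. RDI at the same dose is then not comparable between A1 and A2 or B, although SAP 5.1 also calls for pooled Part A tables.
- Deleting above-limit results removes the highest concentrations, so any bias is downward and falls mainly on the top doses. Derived Cmax and AUC feed the dose-proportionality analysis (SAP 5.7.2.4). SAP 5.6.7 predicts the mean QTcF change "where plasma concentration is specified as the geometric mean" Cmax of each dose level, for a drug whose QT risk the protocol acknowledges (2.2.1.6). A flattened exposure curve would also resemble saturation, which Protocol 6.1.1 gives among its reasons for exploring twice-daily dosing ("eg, due to short half-life, saturation of exposure").

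**Working it through.** The SAP gives formulas here but no numerical results, so there is no stated figure to reproduce. Each formula is applied literally.

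**Disease duration.** Let consent fall at fraction u of its year and diagnosis at fraction v of its year.
- True time = year difference + u − v. Derived time = year difference + 1. Error = 1 − u + v, so an individual error lies between 0 and 2 years.
- Both dates spread evenly (mean u = mean v = 0.5): mean error 1 − 0.5 + 0.5 = 1.0 year.
- All consents in July to December (mean u = 0.75): 1 − 0.75 + 0.5 = 0.75.
- All consents in January to June (mean u = 0.25): 1 − 0.25 + 0.5 = 1.25.
- A simulation of 1,000,000 date pairs agrees (1.00, 0.75 and 1.25). Age at diagnosis comes out 1.0 year too young on average.

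**RDI.** Consider a Part A1 once-daily patient who takes the Day −3 dose and then every one of N daily doses from C1D1 at one dose level.
- Doses taken = N + 1. Duration = N + 3, because Days −2 and −1 are undosed by plan. RDI = (N + 1)/(N + 3).
- N = 21: 22/24 = 91.7%. N = 42: 43/45 = 95.6%. N = 84: 85/87 = 97.7%. N = 365: 366/368 = 99.5%.
- Dose intensity in mg/day falls by the same factor: at 50 mg after one cycle, 50 × 22/24 = 45.8 mg/day.
- Twice-daily patients have no lead-in (Protocol 8.3.1 and Table 14): N/N = 100%.

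**Above-limit results.** The documents give no human concentrations, so this is an illustration under stated assumptions: a one-compartment profile (absorption rate 0.8/h, half-life 15 h), dose-proportional exposure, the post-dose lead-in times of Protocol Table 13, and values above 1000 ng/mL deleted. The slope is the power-model slope for Cmax over the six planned doses; its true value is 1.00.

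| Assumed true Cmax at 700 mg (ng/mL) | Derived Cmax | Derived Tmax (true 4 h) | AUClast, % of true | Slope |
|---|---|---|---|---|
| 800 | 800 | 4 h | 100 | 1.00 |
| 1500 | 959 | 1 h | 82 | 0.88 |
| 3000 | 413 | 48 h | 21 | 0.37 |

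The distortion can therefore go beyond a ceiling. In the third row a higher true exposure yields a lower derived Cmax than in the second. If no sample exceeds the limit, nothing changes.

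**The case against.** **On above-limit results** the other side is strong. The rule acts only on results the laboratory reports as above the limit. Protocol 8.2 leaves the analytical detail to a bioanalytical protocol that is not among the documents; if that protocol provides for dilution and re-assay, no such result need arise. SAP 5.7.2.1 also has each profile checked for suitability before AUC and half-life are calculated, so interpolating AUC under a deleted peak is not automatic. Above-limit results stay visible in the individual listings, and summaries with less than half the data are omitted or flagged. All of that stands. What remains is that the suitability check does not extend to Cmax or Tmax. The acceptance criteria in 5.7.2.2 look only at the terminal phase and the extrapolated AUC.

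A reader might infer from the mouse data that human samples will exceed the limit. At 20 mg/kg, total AUC0-24 of 86 µM·h averages 86/24 = 3.58 µM. Dividing by 1.192 to 1.253 for the metabolite gives 3.01 to 2.86 µM of parent, against a limit of 2.5 to 1.67 µM for an assumed molecular weight of 400 to 600. The documents do not support that step: they give neither a human exposure nor a molecular weight. Their human target, a total trough of 40.3 nM (Protocol 4.2.1), is only about 16 to 24 ng/mL at the same assumed weights. A trough does not rule out high peaks, but it does not establish them either.

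A reader might also infer that the top of the range drops out of the concentration-QTcF model, or that a depressed Cmax would by itself lead to twice-daily dosing. SAP 5.6.7 does not cite the missing-value rule for the model data, and Protocol 6.1.1 requires discussion and agreement between investigators and the sponsor.

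**On RDI**, a reader might infer that no A1 patient can reach 100%. That is too broad. Twice-daily patients are unaffected, and a patient who takes only the lead-in dose scores 1/1. With intra-patient escalation RDI can exceed 100% if the planned dose stays at entry level, which the SAP leaves undefined: 50 to 100 mg from day 22 gives (50 × 22 + 100 × 21)/(45 × 50) = 142% at day 42.

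**On disease duration**, year-only arithmetic might be defended because diagnosis dates are often incomplete. That would not justify adding one: without it, the mean error is zero when dates are spread over the year.

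**Conclusion.** Two derivations give wrong values as written, and a third is a conditional gap.

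- **Disease duration:** overstated by about 1 year on average (0.75 to 1.25 by timing of consent; 0 to 2 individually). Time since first metastasis has the same error, and age at diagnosis is about 1 year too young. These are descriptive baseline rows, and no decision in the SAP uses them.
- **RDI:** too low by 8.3 points after one cycle and 2.3 after four, shrinking with time. This holds for once-daily A1 patients with the lead-in who continue at one dose level.
- **Above-limit results:** if the laboratory reports any, derived Cmax cannot exceed 1000 ng/mL. Cmax and Tmax are then distorted, and possibly AUC, the dose-proportionality slope and the QTcF prediction at geometric mean Cmax. Whether this will occur, and how far, cannot be judged from the documents.

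None of the three affects ORR, the DLT rule or the sample size. They should be corrected before database lock, but they do not threaten the trial's main conclusions.

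**What to change.** - **SAP 5.3.3:** compute both durations as (consent date − event date)/365.25, state a rule for partial dates, and derive age at diagnosis from the result.
- **SAP 5.6.1.1:** keep the assigned dose level in the denominator, but exclude the undosed days between the lead-in dose and C1D1 from the planned dosing days. The one-cycle patient then scores 22/22 = 100%, and dose reductions still lower RDI. A denominator built from the doses currently prescribed should be avoided, because a reduced patient would score close to 100%. State also which dose level counts as planned after intra-patient escalation.
- **SAP 5.7.1.1 and 5.7.2.1:** state that above-limit samples are re-assayed after validated dilution. Where that is impossible, do not treat the result as missing when deriving Cmax, Tmax or AUC; flag those parameters as censored (at or above the limit). Report the number of affected profiles per dose level beside the dose-proportionality and QTcF results. Simply dropping those profiles would remove the highest exposures and, with the minimum of three values per dose level in 5.7.2.4, could remove the top dose altogether.

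The cost is SAP wording and the reprogramming of three derivations. Re-assay, if needed, uses samples already collected. No visit, procedure or treatment rule changes.
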